# 4.4.2.1 Key Secondary Endpoints for EMA

The following endpoints are considered key secondary endpoints for purpose of the marketing authorization application for EMA:

- Change from baseline in BCVA score averaged over Week 36 and Week 40
- Change from baseline in BCVA score averaged over Week 44 and Week 48
- Change from baseline in BCVA score averaged over Week 88 and Week 92

The hypothesis testing for these endpoint will be gated on achieving NI for the primary endpoint test at a 4.5 letter margin as per Section 4.4.1. A fixed sequence testing

procedure will be used to control the type I error rate. The NI tests for the key secondary endpoints will be performed in the order shown above with a NI margin of 3.9 letters, proceeding sequentially and testing each after achieving NI on the previous endpoint. Analysis of these key secondary endpoints will follow the same method as the analysis of the primary endpoint (see Section 4.4.1) in all respects except for the NI margin and timepoints included in the analysis. The two supplementary analyses for using different handling rules for intercurrent events (Section 4.4.1.1) and the per protocol sensitivity analysis (Section 4.4.1) used in the analysis of the primary endpoint will also be conducted for the key secondary endpoints.

Additionally, to address feedback from the EMA, sensitivity analyses will be conducted for each of the above 3 endpoints based on the complete cases in the Per Protocol Population. These analyses include only patients in the Per Protocol Population with BCVA assessments available at both study visits for a particular endpoint (e.g., patients needed to have BCVA assessments at both Weeks 36 and 40 for change in BCVA averaged over Weeks 36 and 40). The analyses will be conducted using the MMRM model as specified in Section 4.4.1, , and using the ANCOVA models with adjustment of treatment group, baseline BCVA score (continuous), and the randomization stratification factor of baseline BCVA (< 74 letters vs. ≥ 74 letters).

# 4.4.2.2 Supplemental Analysis to Assess COVID-19 Impact

Additional supplemental analyses incorporating intercurrent events related to COVID-19 will be used to assess the impact of COVID-19. Previous assessments of the impact of COVID-19 in the Primary and Update CSRs concluded that the impact of COVID-19 on the efficacy findings through Week 48 was minimal; therefore, the additional analyses will only be performed on the following endpoints after Week 48: change in BCVA averaged over Week 60 and Week 64, change in BCVA averaged over Week 88 and Week 92, and change in BCVA over time through Week 96.

The estimand for the additional supplemental analyses is defined as follows:

- Population: Adult patients with nAMD diagnosed within 9 months and receiving at least 4 anti-VEGF intravitreal injections (with the last injection being ranibizumab), responsive to prior anti-VEGF treatment
- Variable: Change in BCVA score from baseline averaged over Week 60 and Week
   64, Change in BCVA averaged over Week 88 and Week 92, and Change in BCVA over time through Week 96
- Intercurrent events:
  - Discontinuation of study treatment due to adverse events (AEs) or lack of efficacy not due to COVID-19: A treatment policy strategy will be applied where all observed values will be used regardless of the occurrence of the intercurrent event
  - Use of any prohibited systemic treatment or prohibited therapy in the study eye (Section 4.4.2 of Protocol) not due to COVID-19: A treatment policy strategy will

be applied where all observed values will be used regardless of the occurrence of the intercurrent event

- Discontinuation of study treatment due to COVID-19: A hypothetical strategy will be applied where all values will be censored after the intercurrent event
- Use of any prohibited systemic treatment or prohibited therapy in the study eye due to COVID-19: A hypothetical strategy will be applied where all values will be censored after the intercurrent event
- Missed dose(s) with potentially major impact on efficacy due to COVID-19, defined according to the treatment arm:
  - Intravitreal arm: two or more consecutive missed visits due to COVID-19 (reported as an intercurrent event at the second consecutive missed visit), or three or more total missed visits due to COVID-19 (reported as an intercurrent event at the third missed visit)
  - PDS arm: any missed refill-exchange due to COVID-19 (reported as an intercurrent event at the missed refill-exchange visit), or missed both supplemental treatment evaluation visits during the refill-exchange interval due to COVID-19

A hypothetical strategy will be applied where all values will be censored after the intercurrent event

- COVID-19 death: A hypothetical strategy will be applied
- Population-level summary: Difference in adjusted mean between PDS 100 mg/mL and intravitreal groups

The analyses will be performed using the same analysis method as the primary endpoint (see Section 4.4.1).

In addition, the COVID-19 related intercurrent events will be summarized by treatment arm.

# 4.4.3 Exploratory Efficacy Endpoints

Exploratory endpoints are:

- BCVA and CST results over time relative to supplemental treatment
- Change from baseline in CST at Week 36
- Change from baseline in CST over time
- Proportion of patients with macular atrophy at baseline, Weeks 36, 48, and 96
- Change from baseline in macular atrophy area at Weeks 36, 48 and 96
- Proportion of patients who gain ≥5 letters in BCVA score from baseline over time.
- Proportion of patients who lose < 15 letters in BCVA score from baseline to the average over Week 88 and Week 92

 Proportion of patients who gain > 15 letters in BCVA score from baseline to the average over Week 88 and Week 92

To evaluate the impact of supplemental treatment with intravitreal ranibizumab on efficacy endpoints for the PDS 100 mg/ml group patients receiving supplemental treatment, graphs by patient showing BCVA and CST over time and indicating times of refill-exchange or supplemental treatments will be provided.

Change from baseline in CST at Week 36 and over time will be analyzed using the same analysis method and data handling rules as the primary endpoint.

Proportion of patients with macular atrophy and macular atrophy area will be analyzed by descriptive summaries including confidence intervals at each timepoint.

The other binary endpoints will be analyzed using the same method as the binary secondary endpoints (see Section 4.4.2).

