• To evaluate the proportion of patients who undergo supplemental treatment with intravitreal ranibizumab 0.5 mg	• Proportion of patients in the implant arm who undergo supplemental treatment with intravitreal ranibizumab 0.5 mg before the first, second, third, and fourth fixed refill-exchange intervals
	• Proportion of patients in the implant arm that undergo a supplemental treatment that requires subsequent additional supplemental treatments during the study

Exploratory Efficacy Objectives	Corresponding Endpoints
• To evaluate the impact of supplemental treatment with intravitreal ranibizumab 0.5 mg	
 
Endpoints will be results-dependent based on number of supplemental treatments
 

 
To evaluate the relative efficacy of ranibizumab delivered via the PDS Q24W with the 100-mg/mL formulation compared with that of 10-mg/mL (0.5- mg dose) Q4W intravitreal ranibizumab injections, as assessed by central subfield thickness on SD-OCT
 
	
 
Change from baseline in CST at Week 36
 
Change from baseline in CST over time
 

 
To assess clinically relevant features using advanced analytics tools (including artificial intelligence-based tools) on multimodal images and clinical data
 
	Clinically relevant features over time

 
To evaluate the development of macular atrophy in patients treated with the PDS Q24W with the 100- mg/mL formulation compared with those with 10-mg/mL (0.5-mg dose) Q4W intravitreal ranibizumab injections.
 
	
 
Proportion of patients with macular atrophy at baseline, Weeks 36, 48, and 96
 
Change from baseline in macular atrophy area at Weeks 36, 48 and 96
 

 
To evaluate the relative efficacy of ranibizumab delivered via the PDS Q24W with the 100-mg/mL formulation compared with that of 10-mg/mL (0.5- mg dose) Q4W intravitreal ranibizumab injections, as assessed by visual acuity
 
	
 
Proportion of patients who gain ≥5 letters in BCVA score from baseline over time.
 

Safety Objective	Corresponding Endpoints

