#### 4.1.1.2 Ocular Inclusion Criteria

Patients must meet the following ocular inclusion criteria for the study eye for study entry:

- Initial diagnosis of exudative nAMD within 9 months prior to the screening visit
- Previous treatment with at least three anti-VEGF intravitreal injections (e.g., ranibizumab, bevacizumab, or aflibercept) for nAMD per standard of care within 6 months prior to the screening visit

If a patient did not receive at least three anti-VEGF injections as described above but is otherwise eligible for the study, the patient can be treated in a runin phase to meet this specific criterion.

• Demonstrated response to prior anti-VEGF intravitreal treatment since diagnosis, as evidenced at screening by the following:

Overall decrease in nAMD disease activity detected on SD-OCT, as assessed by the investigator and confirmed by the central reading center

and

Stable or improved BCVA

- BCVA of 34 letters or better (20/200 or better approximate Snellen equivalent), using ETDRS chart at a starting distance of 4 meters (see the BCVA manual for additional details) at screening and randomization visits
- All subtypes of nAMD lesions are permissible (i.e., type I, type II, type III, or mixed forms per OCT classification)

nAMD lesions at the time of diagnosis must involve the macula (6-mm diameter centered at the fovea).

• Sufficiently clear ocular media and adequate pupillary dilation to allow for analysis and grading by the central reading center of FP, FA, FAF, and SD-OCT images

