#### Study Eye

- Subretinal hemorrhage that involves the center of the fovea, if the hemorrhage is greater than 0.5-disc area (1.27 mm^2) in size at screening
- Subfoveal fibrosis or subfoveal atrophy

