## 4.4.2 Secondary Efficacy Endpoints

Descriptive summaries will be provided for all secondary endpoints based on all observed data. The secondary endpoints are:

- 1. Change from baseline in BCVA score averaged over Week 60 and Week 64.
- 2. Change from baseline in BCVA score over time.
- 3. Proportion of patients with BCVA score of 38 letters (20/200 approximate Snellen equivalent) or worse at the average over Week 36 and Week 40.
- 4. Proportion of patients with BCVA score of 38 letters (20/200 approximate Snellen equivalent) or worse over time.
- 5. Proportion of patients with BCVA score of 69 letters (20/40 approximate Snellen equivalent) or better at the average over Week 36 and Week 40.
- 6. Proportion of patients with BCVA score of 69 letters (20/40 approximate Snellen equivalent) or better over time.
- 7. Proportion of patients who lose < 10 or < 5 letters in BCVA score from baseline to the average over Week 36 and Week 40.
- 8. Proportion of patients who lose < 10 or < 5 letters in BCVA score from baseline over time.
- 9. Proportion of patients who gain ≥0 letters in BCVA score from baseline to the average over Week 36 and Week 40.
- 10. Proportion of patients who gain ≥0 letters in BCVA score from baseline over time.
- 11. Change from baseline in CPT assessed by central imaging vendor with boundaries ILM to inner third of the retinal pigment epithelium (RPE) at Week 36.
- 12. Change from baseline in CPT assessed by central imaging vendor with boundaries ILM to inner third of the RPE over time.
- 13. Proportion of patients in the PDS 100 mg/ml group who undergo supplemental treatment of intravitreal ranibizumab before the first, second, third, and fourth fixed refill-exchange intervals.
- 14. Proportion of patients in the PDS 100 mg/ml group that undergo a supplemental treatment that requires at least one additional supplemental treatments during the study.

The estimand for the binary secondary endpoints are defined as follows:

- Population: Adult patients with nAMD diagnosed within 9 months and receiving at least 4 anti-VEGF intravitreal injections (with the last injection being ranibizumab), responsive to prior anti-VEGF treatment.
- Variable: Proportion of patients for event of interest
- Intercurrent events: Regardless whether or not a patient has the following intercurrent event prior to visit for endpoint:
  - Receives more than 1 supplemental treatments

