  - Receives any prohibited systemic treatment or prohibited therapy in the Study eye (Section 4.4.2 of the Protocol)
  - Discontinuation study treatment due to AEs
  - Discontinuation study treatment due to lack of efficacy as per investigator's clinical judgment.
- Population-level summary: Difference in proportions between PDS 100 mg/ml and intravitreal groups

The proportion of patients in each treatment group and the overall difference in proportions between treatment groups will be estimated using the weighted average of the observed proportions and the differences in observed proportions over the strata defined by randomization stratification factor of baseline BCVA (< 74 letters vs. ≥ 74 letters) using the Cochran-Mantel-Haenszel (CMH) weights (Cochran 1954; Mantel and Haenszel 1959). All observed measurements will be included in the analysis regardless whether or not a patient has an intercurrent event. Confidence intervals of the proportion of patients in each treatment group and the overall difference in proportions between treatment groups will be calculated using the normal approximation to the weighted proportions (Mehrotra and Railkar 2000). If the response rate is low, an unstratified analysis may also be performed.

In addition, the binary secondary endpoints through Week 40 will also be summarized using the same approach with missing assessments imputed with the last post-baseline observation carried forward (continuous BCVA values are carried forward and then the binary endpoint is derived).

Different strata will be used for the CMH analyses of the following binary endpoint:

Proportion of subjects with a BCVA score of 69 letters (approximate 20/40 Snellen equivalent) or better at the average over Weeks 36 and 40: the difference between the two treatment groups will be estimated using the same approach stratified by baseline BCVA (Snellen equivalent of 20/40 or better vs. worse than 20/40).

The continuous secondary endpoints will be summarized using descriptive statistics based on all observed data. These continuous endpoints will also be analyzed following

the same method as the analysis of the primary endpoint (see Section 4.4.1) with the independent variable, baseline BCVA score (continuous), in the model replaced with the baseline value of the corresponding endpoint (e.g., baseline CPT). The intercurrent events and data handling rules for the primary endpoint will apply here.

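### The macular atrophy objective asks about development, but SAP 4.4.3 counts prevalence, so eyes that enter with non-subfoveal atrophy dilute the arm comparison

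*SAP*

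**What the plan says.** Protocol Section 2, Table 1 states the exploratory objective: "To evaluate the development of macular atrophy in patients treated with the PDS Q24W", compared with monthly intravitreal ranibizumab. Two endpoints serve it, and SAP Section 4.4.3 carries both. The binary one is "Proportion of patients with macular atrophy at baseline, Weeks 36, 48, and 96". The other concerns lesion size and reads "Change from baseline in macular atrophy area at Weeks 36, 48 and 96".

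The method is one sentence in the same section: "Proportion of patients with macular atrophy and macular atrophy area will be analyzed by descriptive summaries including confidence intervals at each timepoint". Neither endpoint is restricted to eyes free of atrophy at baseline, and no within-eye comparison with baseline status is planned for the binary endpoint.

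The only study-eye exclusion on atrophy, in Protocol Section 4.1.2.2, is "Subfoveal fibrosis or subfoveal atrophy". Protocol Section 3.1 says that the central reading center's masked eligibility assessment at screening covers macular atrophy.

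A smaller overlap exists for vision. Protocol Section 4.1.1.2 admits eyes at 34 letters or better, and a secondary endpoint in SAP Section 4.4.2 is "Proportion of patients with BCVA score of 38 letters (20/200 approximate Snellen equivalent) or worse at the average over Week 36 and Week 40".

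**The concern.** Development means new atrophy. A prevalence count at Week 96 adds two groups together: eyes that acquired atrophy on study, and eyes that had it at entry. The second group says nothing about whether treatment causes new atrophy, but it enters both the estimate and its variance.

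The area endpoint does not fill the gap. A positive mean change can come from old lesions enlarging, from new lesions, or from both. Subtracting the baseline proportion from the Week 96 proportion gives net new atrophy only if the same gradable eyes contribute at both visits and atrophy does not reverse. The SAP does not plan that comparison.

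What is at stake is the readability of one exploratory comparison. Dilution pulls the arms together, so similar Week 96 prevalences could be read as similar rates of new atrophy when the plan contains no measure of that rate.

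**Working it through.** **The plan's own figure.** No sample size, power, baseline prevalence or incidence is stated for macular atrophy. The only sizing figure, at least 90% power for the primary endpoint (SAP Section 2.2), does reproduce: after both 10% allowances, non-inferiority power is 90.9% and equivalence power 90.5% at one-sided 0.025. It has no bearing on this point.

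**Inputs from the documents.** 418 patients enrolled, 3:2 allocation, confidence level 95.03% (SAP Sections 2.2 and 4.4). The split is derived: 418 × 3/5 ≈ 251 implant and 418 × 2/5 ≈ 167 intravitreal. The normal multiplier for 95.03% is 1.963.

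**Assumptions, not in the documents.** Baseline prevalence b, equal in both arms in expectation; proportions i₁ (implant) and i₂ (intravitreal) of atrophy-free eyes with new atrophy by Week 96; existing atrophy persists; no missing images.

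**Formulas.**

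- Prevalence in an arm: p = b + (1 − b)i
- Difference in prevalence: p₁ − p₂ = (1 − b)(i₁ − i₂)
- SE for prevalence: √[p₁(1 − p₁)/251 + p₂(1 − p₂)/167]
- SE for incidence: √[i₁(1 − i₁)/(251(1 − b)) + i₂(1 − i₂)/(167(1 − b))]

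**Worked case**, b = 20%, i₁ = 10%, i₂ = 20%:

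- p₁ = 0.20 + 0.80 × 0.10 = 0.28; p₂ = 0.20 + 0.80 × 0.20 = 0.36; difference 8 points.
- SE = √(0.2016/251 + 0.2304/167) = 4.67 points; CI half-width 1.963 × 4.67 = 9.2 points.
- Incidence among 200.8 and 133.6 eyes at risk: difference 10 points; SE = √(0.09/200.8 + 0.16/133.6) = 4.06 points; half-width 8.0 points.

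**Range over b** (difference ± CI half-width, in points):

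| Baseline prevalence | New atrophy 10% vs 20%: prevalence | New atrophy 10% vs 20%: incidence | New atrophy 5% vs 10%: prevalence | New atrophy 5% vs 10%: incidence |
|---|---|---|---|---|
| 5% | 9.5 ± 7.8 | 10 ± 7.3 | 4.8 ± 6.5 | 5 ± 5.4 |
| 10% | 9.0 ± 8.4 | 10 ± 7.5 | 4.5 ± 7.4 | 5 ± 5.6 |
| 20% | 8.0 ± 9.2 | 10 ± 8.0 | 4.0 ± 8.6 | 5 ± 5.9 |
| 30% | 7.0 ± 9.6 | 10 ± 8.5 | 3.5 ± 9.4 | 5 ± 6.3 |

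In all eight scenarios the incidence measure has the larger difference and the narrower interval, despite its smaller denominator.

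**Chance imbalance.** The baseline difference between arms has SD √[b(1 − b)(1/251 + 1/167)]: 2.2 points at b = 5%, 3.0 at 10% and 4.0 at 20%. The planned summary does not adjust for it.

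**Vision overlap.** Entry at 34 or more and an outcome of 38 or less share the scores 34 to 38. If baseline BCVA is taken as normal and truncated at 34, with mean/SD anywhere from 74/10 to 65/15 (assumed), the share in that window is about 0.02% to 2.1%, or roughly 0 to 9 of 418 eyes.

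**The case against.** The strongest defence is that the gap is small. The analysis is exploratory and descriptive, so no planned decision turns on it. The same row reports the baseline proportion, so a reader can see how many eyes were positive at entry. In an eye free of atrophy at entry, any area gained is new. This all stands, and it limits the weight of the point. It does not supply the missing number: no planned output isolates the atrophy-free eyes.

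It is also fair that the table rests on assumed rates, that an incidence denominator too loses eyes without gradable Week 96 images, and that SAP version 3 was written after the Primary and Update CSRs, with its changes aimed at data after Week 48. Only the Week 96 analysis can still be specified ahead of reporting.

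A reader might infer three stronger things that the documents do not support:

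- *That the comparison is biased toward one arm.* Randomization balances atrophy at entry in expectation.
- *That the 38-letter endpoint also fails its objective.* Its objective in Protocol Table 1 is relative efficacy by visual acuity, not new events. A proportion in a vision category is a valid randomized comparison for that, and eyes at 34–38 letters can improve. Within-patient loss is covered by other endpoints, including change from baseline and loss of fewer than 10 or 5 letters.
- *That the SAP acknowledges the problem by stratifying the 69-letter endpoint at Weeks 36 and 40 at 20/40.* SAP Section 4.4.2 gives no reason for those strata. A baseline stratum at or below 38 letters would probably hold very few eyes.

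**Conclusion.** The point holds for macular atrophy. The objective is development, the binary endpoint is prevalence, the entry criteria let prevalent cases in, and the area endpoint does not separate new lesions from growth. The consequence is an arm difference shrunk by the factor (1 − b), plus uncorrected chance imbalance at baseline. The form of that factor rests only on existing atrophy persisting and being balanced in expectation. Its value cannot be stated, since b is not in the documents: under the assumed range of 5% to 30%, the shrinkage runs from 5% to 30% of the true difference.

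The endpoint is exploratory, and the primary and EMA key secondary conclusions do not depend on it. The 34–38 letter overlap is a minor reporting matter.

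**What to change.** In SAP Section 4.4.3, add as the measure for the development objective: the proportion with new macular atrophy at Week 96 among study eyes graded free of macular atrophy at screening, by arm, with the arm difference and its 95.03% CI. Keep the prevalence row as context. Show Weeks 36 and 48 in the same way, labelled post hoc because reporting through Week 48 was complete when SAP version 3 was written.

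For SAP Section 4.4.2, endpoints 3 and 4, report the number of eyes at 34–38 letters at baseline by arm. As a supportive row, add the proportion at 38 letters or worse among eyes above 38 at baseline. The existing endpoint stays as it is.

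Cost: SAP wording and one baseline-defined subset per endpoint, with no new data. The schedules in Protocol Appendices 1 and 2 already include fundus photography, fluorescein angiography and autofluorescence at screening and Weeks 36, 48 and 96, and the reading center assesses atrophy at screening. The downside is that the denominator loses every eye with atrophy at screening. At b = 20%, that is about 50 of 251 and 33 of 167 eyes, so the loss may be more than slight.

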## 4.4.4 Patient-Reported Experiences

Patient preference will be assessed using the PDS Patient Preference Questionnaire (PPPQ). The PPPQ is a 3-item questionnaire that captures a patient's preference for treatment, the strength of their preference, and the reasons for their preference. The PPPQ will be administered only to patients in the PDS 100 mg/ml arm, who received intravitreal anti-VEGF treatment prior to Day 1. The PPPQ specifically assesses patient preference for treatment and could demonstrate a benefit of PDS over monthly intravitreal ranibizumab 0.5 mg due to less frequent treatments and the advantage of a refill-exchange over injection. However, due to the nature of the clinical trial, monthly visits are required so study participants will not experience the advantage of less frequent visits. The strength of preference and reasons for preference will be summarized descriptively.

The Macular Disease Treatment Satisfaction Questionnaire (MacTSQ) was developed to provide a means of evaluating satisfaction with therapies for macular disease. The MacTSQ provides a total score and two subscale scores: impact of treatment, and information provision and convenience. Higher scores for the total scale and the subscales represent increased satisfaction with treatment.

The MacTSQ score, including both total score and subscale scores at scheduled visits, will be summarized using appropriate descriptive statistics based on the observed data. The MacTSQ will be scored per the instructions in the "Summary of the MacTSQ rev11.8.15." Subscale 1 (Information provision and convenience) contains six items (1, 9, 10 to 13). Item scores are summed to give a subscale score between 0 and 36. Subscale 2 (Impact of treatment) contains six items (items 2 to 6, 8). After recoding item 2 and 3 per the instructions, item scores are summed to create a subscale score

between 0 and 36. The total score is calculated by combining the 12 items from the two subscales, and ranges from 0 to 72.

Data will be specifically imputed using the rules as follows:

- Subscale 1 (information provision and convenience): Set the subscale 1 value to missing if any of the 6 items in the subscale are missing.
- Subscale 2 (impact of treatment score): Set the subscale 2 value to missing if two or more of the 6 items in the subscale 2 are missing. If only one item is missing, impute the item value based on the average of the other five items.
- Single scale (overall score): Set the single scale value to missing if four or more of the 12 items are missing. If three or less items are missing, impute the missing item values based on the average of the other available items.

